Introduction. Malnutrition is recognized as a major concern by healthcare providers, as well as by patients, families, and caregivers. In a very recent survey, 28% of 1,035 patients, families and caregivers reported that malnutrition was a very significant problem, while 55% reported it was a somewhat significant problem in older adults 65 and older.²⁶ This response aligns with reports that up to 65% of older adults admitted to the hospital are malnourished (National Resource Center on Nutrition, Physical Activity, and Aging, 2015). Thus, it is essential to establish systematic malnutrition screening in the clinical setting and to develop intervention models and standards of nutritional care. The objective of this aim is to investigate the feasibility, fidelity and acceptability of a nutrition intervention protocol providing higher protein intakes before and after surgery in malnourished Veterans. To achieve the objective of this aim, we will test our working hypotheses that recruitment in clinic will have a high yield and that intervention fidelity (adherence, retention) and acceptability (attrition, patient satisfaction) will be predominantly satisfactory. The rationale for this aim is that successful completion of the proposed research will provide necessary knowledge to begin to identify feasible and acceptable interventions for community-dwelling Veterans who are preparing for surgical procedures. When the proposed studies for Aim 1.1 have been completed, it is our expectation that $\geq 75\%$ of patients approached for recruitment will agree to participate, $\geq 75\%$ of the time patients will adhere to the intervention, $\geq 80\%$ of the participants will remain in the study, and that $\geq 80\%$ of participants will find the intervention to be acceptable. Such findings would be of considerable importance, providing a patient-centered viewpoint that will inform the development of nutrition interventions that meet the standards and needs of high-risk Veteran Populations.

Specific Aim 1.2 – *To determine the effect size for planned future studies of enhanced protein supplementation in malnourished Veterans, with physical function as the primary outcome of interest. Of secondary interest are: biomarkers of inflammation (albumin, hsCRP, TNF- α , IL-6), dietary intake, hospital readmission, discharge location, length of skilled care, and ED admission, and physical activity.*

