Measures and Data Collection Points

| Measure | When Collected |
|------------------------------------|-----------------------|
| NSR-2002 | Baseline (T1), T2, T3 |
| PG-SGA | T1, T2, T3 |
| Nutrition Focused Physical Exam | T1, T2, T3 |
| Cognition | T1 |
| Medical History | T1 |
| Demographic | T1 |
| Anthropometrics | T1, T2, T3 |
| Comorbidity Status | T1 |
| Bristol Stool Chart | T1 |
| Short Physical Performance Battery | T1, T2, T3 |
| Handgrip strength | T1, T2, T3 |
| Biological Markers | T1, T2, T3 |
| Postoperative outcomes | T3 |

| | |
|---|----------------------------|
| Physical Activity | T1, T2, T3 |
| PROMIS and PROMIS GLOBAL QUESTIONNAIRES | T1, T2, T3 |
| Three-day Food Record | T1, T2, T3 |
| Protein Checklist | Daily |
| 24-Hour Dietary Recall | Weekly between time points |
| Participant Satisfaction Questionnaire | T3 |
| Participant Acceptability | T3 |

Risk/Benefit Assessment

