- Patient satisfaction will be assessed by a brief 5-item questionnaire: a) satisfaction with participating in the study; b) satisfaction with directions on how and when to consume the protein supplement, c) satisfaction of the taste of the protein supplement, d) satisfaction with functional status after protein e) satisfaction with interactions with the registered dietitian. $\geq 80\%$ of participants will report satisfaction with participating in the study.

2. Qualitative semi-structured interviews in a subset of the participants. A qualitative analytical approach is well suited to exploring concepts related to a complex process (malnutrition and nutrition intervention). We anticipate we will achieve thematic saturation by enrolling 20 participants. The data in the interview transcripts will be coded using Atlas software. Perform the analysis using the skills obtained in my proposed coursework and with the assistance from my co-investigators. Data analysis will include summarizing the major topics of discussion, synthesizing recurring themes, and selecting exemplars of these themes from individual comments. In concert with the quantitative results, these data will be used to inform the design of a larger trial aimed at improving outcomes for older, malnourished Veterans.

- Patients will be selected using maximum variation purposive sampling including to include a mix of ages, genders, races, surgical procedures, and nutrition status.
- Each semi-structure interview will be conducted at the endpoint visit and will last approximately 15 minutes. The interviews will be conducted according to a script developed in close collaboration with my co-investigators.
- All interviews will be tape-recorded and transcribed. The interviewer will also take written notes to capture changes in emotion or enthusiasm related to the response to each question that will not be captured in transcribed reports.

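### The 80% acceptability criterion is scored on satisfaction with taking part in the study, not on the intervention that Aim 1.1 names

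*Combined protocol and SAP*

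**What the plan says.** The introduction to Specific Aim 1.1 sets the target: at least 80% "of participants will find the intervention to be acceptable". It describes acceptability as made up of attrition and patient satisfaction.

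The matching analysis is in the section headed Aim 2.1 Analysis Plan. It assesses acceptability by attrition, a five-item satisfaction questionnaire and semi-structured interviews in a subset. The one numeric criterion under that heading is that at least 80% of "participants will report satisfaction with participating in the study". This repeats the first questionnaire item, "a) satisfaction with participating in the study".

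Three further items concern the supplement: "b) satisfaction with directions on how and when to consume the protein supplement"; "c) satisfaction of the taste of the protein supplement"; and (d), satisfaction with function following the protein. Item (e) concerns contact with the dietitian. None of (b) to (e) has a threshold, and no rule combines them with (a).

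The table of measures also has a row "Participant Acceptability | T3", separate from the satisfaction questionnaire. The analysis plan does not describe a measure of that name.

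**The concern.** The target and the criterion share the 80% figure but name different objects: the intervention in the aim, taking part in the study in the analysis. The questionnaire itself treats these as different things, since it asks about the supplement separately. Satisfaction with taking part can also reflect the weekly calls and the payment of up to $160, neither of which is the protein regimen.

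The criterion also leaves the arm open. PeriHab takes 30 g of protein three times a day for two weeks before and four weeks after surgery. Controls take one oral supplement a day, before surgery only, so they cannot judge the tested regimen. Elsewhere the plan does separate the arms: the adherence hypothesis is arm-specific, and retention and adherence get confidence intervals overall and by group. Acceptability gets neither.

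Acceptability is one of the three properties the pilot is meant to evaluate, and its results are to inform the larger trial. A reported success on the 80% figure would be read as a statement about the regimen.

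**Working it through.** The plan gives no calculated figure for this criterion, so there is none to reproduce. The check is what the criterion, as written, allows.

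**Inputs.** 42 per arm and 84 in total (Design; Study Arms); 80% threshold (Specific Aim 1.1 and Aim 2.1 Analysis Plan). I assume that all 84 completers answer the questionnaire at T3.

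**1. Dependence on the supplement items.** Only item (a) counts. Items (b), (c) and (d) could each be 0/42 in PeriHab and the criterion could still be met. This needs no assumed rates.

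**2. Item (a), if the arms are pooled.**
- Count needed: 0.80 × 84 = 67.2, so 68.
- 68/84 = 81.0%, exact (Clopper-Pearson) 95% CI 70.9% to 88.7%.
- If all 42 controls are satisfied, PeriHab needs 68 − 42 = 26, and 26/42 = 61.9%.

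**3. A supplement item in PeriHab only.**
- Count needed: 0.80 × 42 = 33.6, so 34.
- 34/42 = 81.0%, exact 95% CI 65.9% to 91.4%.

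**4. Chance of meeting each criterion (binomial; the true rates are assumed, since the documents give none).**

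| Criterion | Assumed true rate | Probability met |
|---|---|---|
| Item (a), at least 68 of 84 | 85% | 0.88 |
| Item (a), at least 68 of 84 | 90% | 0.996 |
| Taste, at least 34 of 42 PeriHab | 50% | <0.001 |
| Taste, at least 34 of 42 PeriHab | 60% | 0.003 |
| Taste, at least 34 of 42 PeriHab | 70% | 0.08 |

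The two criteria can therefore give opposite answers in the same trial.

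**5. Participants who refuse the supplement.** The withdrawal section removes them, the questionnaire is given at T3, and enrolment runs until 84 have completed. Refusers may therefore be replaced and never asked. Let w be the number of PeriHab refusers withdrawn in addition to the 42 completers, each counted as not finding the supplement acceptable. I take w from 0 to 10 because 42/52 = 80.8%, about the plan's own retention target.

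| w | Denominator | 34 satisfied gives | Count needed for 80% |
|---|---|---|---|
| 0 | 42 | 81.0% | 34 |
| 5 | 47 | 34/47 = 72.3% | 0.80 × 47 = 37.6, so 38 |
| 10 | 52 | 34/52 = 65.4% | 0.80 × 52 = 41.6, so 42 |

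The handling of refusers can thus move the result as much as the choice of item.

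**The case against.** The strongest reply is that acceptability does not hang on one question. The aim itself describes it through attrition and satisfaction, and the analysis adds interviews that are to be read together with the quantitative results. Dislike of the supplement has other outlets: PeriHab adherence is counted from empty containers against a 75% hypothesis, retention has an 80% hypothesis, and withdrawing refusers raises attrition. The 80% is called an expectation, and no go/no-go rule is tied to it.

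Most of this stands, and it rules out several stronger readings:

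- A reader might infer that dislike of the supplement would go unseen, or that the whole acceptability conclusion rests on item (a). The documents do not support that. What remains is narrower: none of these other sources enters the 80% criterion, attrition has no threshold under acceptability, and the interviews (about 20 participants) have no decision rule.
- A reader might infer that controls are certain to be counted. The text says only participants, in the aim as well as in the criterion, and gives no pooling rule. The 26/42 figure is conditional on pooling.
- A reader might infer that controls have no supplement to judge. They take one a day before surgery, so items (b) and (c) can be put to them, though not about the PeriHab regimen.
- A reader might take the "Participant Acceptability | T3" row as a ready replacement. It is undescribed and may simply be the subset interviews.

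The reply does not remove the mismatch. Describing acceptability partly as satisfaction does not say satisfaction with what, and the aim names the intervention.

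**Conclusion.** The point holds in this form: the only numeric acceptability criterion measures something other than what Aim 1.1 names, so acceptability could be declared met while the plan's own supplement items say otherwise.

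That the result is independent of items (b) to (d) follows from the text alone. The 62% figure rests on pooling the arms and on every control being satisfied. The probabilities rest on assumed rates, and nothing in the documents shows how far study satisfaction and supplement satisfaction would diverge.

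No safety or efficacy inference depends on this. It should still be corrected, because it decides what the pilot can claim about one of its three stated objectives.

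**What to change.** In the acceptability part of the Aim 2.1 Analysis Plan:

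1. Apply the 80% criterion in the PeriHab arm to one supplement-specific item named in advance, for example item (c), "satisfaction of the taste of the protein supplement", with an exact 95% confidence interval. State which responses count as satisfied. Report items (b) and (d) alongside.
2. Count randomized PeriHab participants withdrawn for refusing the supplement as not finding it acceptable, at least in a sensitivity analysis, and give the number.
3. Report item (a) by arm, as general satisfaction with the study.
4. Do not attach the criterion to the Participant Acceptability row unless that measure is first defined and shown to be collected from the whole arm.

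No new data are needed for the questionnaire items; the refusers come from withdrawal records. The costs are an interval based on 42 rather than 84 (at the threshold, 25.5 percentage points wide, 91.4 − 65.9, against 17.8, 88.7 − 70.9) and a figure that may be less favourable. Taste alone is also only part of acceptability, which is why (b) and (d) belong beside it.

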Introduction. Older adults have reduced adaptive and regenerative capacities to recovery from a surgical insult.²⁷ Thus, when coupled with insufficient energy intake, malnutrition becomes the driver that leads to further deterioration of functional abilities, reduction in lean muscle mass, and inability to maintain physical reserve. A generous and balanced intake of high quality protein (~30 grams) is essential for achieving optimal protein synthesis in older adults²⁸ and is linked to lean mass retention.²⁹ The essential amino acids

found in complete (animal) proteins stimulate translation initiation of the mTOR signaling pathway and increase muscle protein synthesis in older individuals.²⁹ The objective of this aim is to research the effects of a meal-based protein enhanced perihabilitation intervention in malnourished older Veterans undergoing elective surgery on the primary outcome physical function and secondary outcomes, inflammatory biomarkers (albumin, hsCRP, TNF- α , IL-6), dietary intake, hospital readmission, discharge location, length of skilled care, and ED admission, and physical activity. To achieve the objective of this aim, we will test the working hypothesis that Veterans consuming the enhanced protein supplementation will have superior improvements in function compared to the control arm. Approach: We will further refine our working hypothesis in a two-armed pilot trial comparing a high protein nutrition supplement for two weeks pre and post-surgery to an education control arm. We will assess physical function (SPPB) and secondary outcomes two weeks before, the day of surgery, and four weeks post-surgery. The successful completion of the proposed research will provide preliminary data to test this hypothesis in a large scale randomized controlled trial. When the proposed studies for Aim 1.2 have been completed, it is our expectation that the protein intervention will prove to provide higher functional and physiological benefits relative to the control treatment, illustrating the importance of nutritional perihabilitation prior and following surgery in high-risk, vulnerable populations.

Design

[figure not shown]
This is a Randomized Controlled Study. Veterans will be enrolled until 84 participants have completed the study.

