Setting: The POSH Clinic is an interdisciplinary collaboration between surgery, anesthesiology, geriatrics, nursing, and physical therapy to provide perioperative surgical care for high-risk Veterans at the Durham VAMC. The clinic opens with a conference to review patients to be seen that day. The surgery chief resident presents and the team covers technical issues with the surgery and selection of anesthesia, as well as covering a list of specific care points. The POSH clinic estimates 200 – 400 patients enrolled annually.

VAPOSH Veterans who are malnourished or at risk of being malnourished will be randomly assigned on a 1:1 ratio by computer-generated random numbers to either an education (nutritional counseling) control (PoshControl) arm or high-protein perihabilitation (PeriHab) arm. All will receive nutrition education. Participants in the PeriHab arm will also be provided with high quality protein supplements that will bring their protein intakes to at least 30 grams for each of the 3 meals per day.

Study Arms:

- PoshControl; n = 42: During their VAPOSH clinic visit, participants will be provided nutrition counseling and prescribed to consume protein at 1.0 g/kg of body weight in the form of educational handouts explained by a Registered Dietitian. Participants will also be instructed to consume 1 oral nutrition supplement per day two weeks before surgery.
- PeriHab; n = 42: PeriHab will be provided nutrition counseling and prescribed to consume protein at 1.6 g/kg of body weight) as well as provided 30 g of high quality protein to some 3 times per day for 2 weeks before and 4 weeks after surgery.

Measurements:

After the participant has been consented and HIPAA Authorization forms have been signed, a Registered Dietitian will administer the NRS-2002 screening tool, the PG-SGA, and nutrition focused physical exam. A patient screening “nourished” on the NRS-2002, PG-SGA, and nutrition focused physical exam will not be included in the study. For study candidates who are malnourished or at nutritional risk we will then proceed with baseline assessments (described below). Upon the completion of all baseline assessments, the participant will be randomized to PeriHab or PoshControl. The following variables will be blocked in this order: 1) surgery type and 2) American Society of Anesthesiology (ASA) Physical Status Classification System (≥ 3 versus < 3). An equal number of participants will be randomized across the two arms.

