Aim 1.2 Analysis Plan: This design is a two-armed clinical trial, with replicate measures at three time points: baseline, two, and six weeks. Since subjects are randomized to either PeriHab or PoshControl arm, and the groups are presumed equal at baseline, the analysis is straightforward. Following the Good Clinical Practice Guidelines for the analysis of a clinical trial, we will employ mixed models,⁴³ analyze under an Intent to Treat (ITT) criteria, and control for baseline and assess the impact of Time, Treatment Group and the interaction of these variables on the outcomes. Relative to the usual repeated measures designs, mixed models have several advantages: 1) missing values present no particular difficulties in estimation and the estimates are unbiased as long as the set of variables leading to MAR are estimated, 2) the usual assumption of conditional independence (compound symmetry) used in standard repeated measures need not be made, and 3) the actual times of measurement need not be equivalent across subjects. Controlling for the individual baseline values for the particular outcomes, the trajectories over time and differences in those trajectories will be assessed. Following the statistical principles section from the International Conference on Harmonization, we will select covariates (e.g., age, race, number of comorbidities) for the primary models a priori, but we also will conduct auxiliary sensitivity analyses that evaluate whether potential group imbalances bias the treatment effect estimate. These analyses will be performed using conventional testing for confounding.

For any particular outcome, the general form of the model will be:

$$Y_{it} = \beta_0 + \beta_1(\text{group}) + \beta_2(\text{time}_t) + \beta_3(\text{group} * \text{time}_t) + \beta_4(\text{covariates}) + \varepsilon_{it}$$

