Where i is an indicator of person, and time is defined as $t=1, 2$ (measuring week 2 or 6), and the β 's are regression coefficients connecting the predictors to the outcome. For brevity, we list β_4 as a vector of K regression coefficients linking the K covariates to the outcome. As defined, the overall test of the intervention effect will be the joint effect of group and group*time on 2 df (β_1 and β_2) assessing an overall effect of group, and if this group effect is constant over time. If significant, follow-up tests will assess where group differences lie. In particular, we note that if the time by group interaction is rejected, we will test if the groups differ at the end of 6 weeks (a test of effect at the completion of the intervention).

We will carefully examine model assumptions, including the distribution of model residuals, additively, linearity, and influential observations, and will, if necessary, re-parameterize the models or transform the outcomes accordingly.

We note that we have listed numerous measures to be analyzed as outcomes, but have listed only 2 domains of outcomes as primary (physical function and a biological index of nutrition status and inflammation). We will not adjust for Type-I error rate for these primary outcomes. Rather, we will warn the reader of the multiple outcomes tested and the chance for a Type-I error.

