The results of these analyses will provide invaluable information regarding the process and functional forms and, potentially, the causal pathways of the intervention process. For example, one important analysis will enter 'level of compliance to the intervention' into the analysis, allowing for a 'per protocol' analysis of the results.

Power Estimate: Estimate effect sizes for the physical function between-group comparisons and the power available to detect effect with two-tailed tests are provided below for the total N= 80. The objective of this pilot study is to perform preliminary evaluation of a nutrition perihabilitation program in malnourished Veterans, in preparation for a larger grant submission. This pilot work will allow us to conduct sample size, effect sizes, and power analyses for a larger clinical trial. To date, no randomized controlled nutrition perihabilitation study has been conducted in malnourished Veterans. As such, we turned to the literature. Gillis et al.,⁴⁶ reported that older adults undergoing colorectal resectioning surgery who were given nutrition supplementation 3 weeks before surgery improved by 23.7 meters on the 6 minute walk test while the arm given nutrition supplement following the surgery declined by -21.3 meters. The pooled standard deviation of these changes was 67.75. Thus, a standard difference of $0.66 = (23.7 - (-21.3))/67.75$ was observed. Differences of this magnitude have been labeled as 'medium' in the statistical power literature (70). Assuming a standard deviation in the change scores of 67.75, n=40 per group, power=80% and alpha=0.05 (two-tailed), we are powered to detect a difference in changes scores of a standardized magnitude of 0.634, in line with the results of Gillis et al.⁴⁶

References

2. Morley J. Decreased food intake with aging. *J Gerontol Med Sci* 2001;56:81-88.

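### The Aim 1.2 model as printed gives the baseline value one slope for both the day-of-surgery and the 4-week post-operative visit; if the true slopes differ, the week-6 group effect is less precise than it could be

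*Combined protocol and SAP*

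**What the plan says.** Function is measured "two weeks before, the day of surgery, and four weeks post-surgery" (Specific Aim 1.2, Approach); these are T1, T2 and T3. In the Aim 1.2 Analysis Plan only weeks 2 and 6 (T2 and T3) are outcome times, so baseline (T1) is adjusted for and is not itself an outcome row: "Controlling for the individual baseline values for the particular outcomes, the trajectories over time and differences in those trajectories will be assessed".

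The equation contains group, time, group-by-time and a covariate term. The covariate coefficient is defined as a "vector of K regression coefficients linking the K covariates to the outcome". That is one coefficient per covariate, with no time index and no covariate-by-time product. Baseline is not written by name in the equation.

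The section says that compound symmetry is not required, but names no covariance structure. The primary test is the joint effect of group and group-by-time. The group difference at 6 weeks is a follow-up test, identified as the effect at completion of the intervention. Re-parameterizing is allowed after the model assumptions have been examined.

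**The concern.** T1 to T2 is about two weeks without an operation, whereas T2 to T3 contains abdominal surgery in high-risk older patients. Baseline SPPB may therefore predict the T2 value well and the T3 value less well. A single slope has to compromise between the two. When the residual variance is smaller at T2 and the fit allows for that, the compromise sits close to the T2 slope, and the T3 values are over-adjusted.

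The precision of the week-6 group difference is at stake. Aim 1.2 is meant to supply an effect size for a larger trial, and this contrast describes the effect at the end of the intervention. The remedy uses data already collected.

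**Working it through.** **The plan's own figure.** The Power Estimate reads "Assuming a standard deviation in the change scores of 67.75, n=40 per group, power=80% and alpha=0.05 (two-tailed"), and concludes that "we are powered to detect a difference in changes scores of a standardized magnitude of 0.634". A two-sample t-test with 40 per group (noncentral t, 78 df) gives a detectable difference of 0.6343, and 79.96% power at 0.634. The normal approximation gives (1.960 + 0.842) × √(2/40) = 0.626. The literature effect is (23.7 + 21.3)/67.75 = 0.664. The figure reproduces. It concerns change scores on the 6-minute walk, so the baseline slope in the SPPB model does not enter it.

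**Inputs for the check.** From the documents: two outcome visits, 1:1 allocation and 84 planned completers. Assumed, because the documents do not give them: the correlations r12 (T1–T2), r13 (T1–T3) and r23 (T2–T3), and k, the T3 SD relative to a common SD of 1 at T1 and T2.

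**Formulas** (large sample, complete data)
- Raw slopes: β2 = r12 and β6 = k·r13.
- Residual covariance after baseline: S22 = 1 − r12²; S66 = k²(1 − r13²); S26 = k(r23 − r12·r13).
- Common slope, unstructured fit: b = β6 + w(β2 − β6), with w = (S66 − S26)/(S22 + S66 − 2·S26).
- Common slope, homogeneous compound-symmetry fit: w = 1/2.
- Excess variance of the week-6 group effect over visit-specific slopes: (b − β6)²/S66.

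**Worked case**, r = (0.85, 0.50, 0.55), k = 1:
- S22 = 1 − 0.7225 = 0.2775; S66 = 0.75; S26 = 0.55 − 0.425 = 0.125.
- w = 0.625/0.7775 = 0.804; b = 0.50 + 0.804 × 0.35 = 0.781.
- Excess = 0.281²/0.75 = 10.6%.
- Compound symmetry: b = 0.675; excess = 0.175²/0.75 = 4.1%.
- k = 1.3: β6 = 0.65, b = 0.831; excess = 0.181²/1.2675 = 2.6%.

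**Range of assumptions** (excess variance)

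| r12, r13, r23 | Unstructured, k = 1 | Unstructured, k = 1.3 | Unstructured, k = 0.8 | Compound symmetry, k = 1 |
|---|---|---|---|---|
| 0.70, 0.70, 0.70 | 0% | 2.6% | 0.6% | 0% |
| 0.80, 0.60, 0.60 | 2.9% | 0.0% | 7.4% | 1.6% |
| 0.80, 0.50, 0.50 | 6.1% | 1.2% | 11.5% | 3.0% |
| 0.85, 0.50, 0.55 | 10.6% | 2.6% | 19.6% | 4.1% |
| 0.80, 0.40, 0.40 | 10.2% | 3.9% | 16.2% | 4.8% |
| 0.85, 0.40, 0.45 | 15.9% | 6.3% | 25.9% | 6.0% |
| 0.90, 0.50, 0.55 | 16.5% | 4.4% | 32.0% | 5.3% |
| 0.80, 0.30, 0.40 | 17.1% | 8.8% | 23.6% | 6.9% |

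Rows 2 to 5 are the moderate cases. The T2–T3 correlation matters a little: (0.80, 0.40, 0.50) gives 11.8% at k = 1. The first row shows that the raw slopes have to match, not the correlations.

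**In other units**, for the moderate cases at k = 1:
- Patients: 84 × 0.029 = 2.4 to 84 × 0.106 = 8.9.
- Width of the confidence interval: √1.029 = 1.014 to √1.106 = 1.052 times.
- If visit-specific slopes gave 80% power, the common slope gives Φ(2.802/√1.029 − 1.960) = 78.9% down to Φ(2.802/√1.106 − 1.960) = 75.9%.

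**Simulation.** Trials of 84 patients (1,500 to 2,000 per setting, unstructured covariance, equal SDs) gave variance ratios of 1.03, 1.05, 1.12 and 1.20 for r = (0.80, 0.60, 0.60), (0.80, 0.50, 0.50), (0.80, 0.40, 0.50) and (0.80, 0.30, 0.40). With week-6 dropout depending on the week-2 value, the last three were 1.06, 1.10 and 1.25. There was no material bias, and test size was about 4% to 6% under both models. Where the slopes were equal or nearly so, ratios as low as 0.994 to 0.998 appeared: the common slope gained well under 1%, within simulation error.

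**The case against.** The strongest reply is that the common slope is an inference. The equation is offered as a general form, baseline is not named in it, and the covariates given as examples are age, race and number of comorbidities. The sentence on controlling for baseline does not say how the slope behaves over time. The plan also promises to check additivity and linearity and to re-parameterize if needed. This is a pilot, and the week-6 contrast only follows up a joint test.

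Part of this stands. The common slope comes from reading the equation together with the definition of its covariate coefficients, which is the plain reading but not an explicit statement. The point affects efficiency, in a follow-up contrast. Re-parameterizing is a weaker answer, because it happens after the data have been examined, while the same section commits to choosing primary-model covariates in advance.

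A reader might infer three stronger things, none of which the documents support:
- **That precision is certain to be lost.** Nothing in the documents shows that the raw slopes differ. A wider spread of function after surgery would bring them closer in several of the cases above, and under compound symmetry the loss is roughly half or less of the unstructured figure.
- **That the treatment effect is biased or the test invalid.** Under randomization a misplaced baseline slope does neither, and the simulations agree.
- **That the stated power is wrong.** The 0.634 reproduces and does not use this model.

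**Conclusion.** The point holds as a conditional efficiency point. On its plain reading the printed model fixes one baseline slope across two visits separated by surgery, and this brings no worthwhile benefit. The cost is more variance in the week-6 group effect if the raw slopes differ, and nothing if they match.

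The size cannot be fixed from the documents. With equal SDs and an unstructured covariance, the four moderate cases give about 3% to 11%. Values above 15% need more extreme inputs: a week-2 correlation near 0.9, a week-6 correlation near 0.3, or 0.85 paired with 0.40. For the same moderate cases the loss is about 0% to 4% if the week-6 SD is 1.3 times the week-2 SD, about 2% to 5% under compound symmetry, and about 7% to 20% if the week-6 SD is 0.8 times. Validity is not in question. This is a small, nearly free improvement to make before the data are analysed.

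**What to change.** In the Aim 1.2 Analysis Plan:
- Write the baseline value of the outcome into the equation by name.
- Add a baseline-by-visit term, so that the fixed part is group, visit, group-by-visit, baseline, baseline-by-visit and the remaining covariates.
- State an unstructured 2x2 within-person covariance for weeks 2 and 6.

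The cost is one extra coefficient with about 84 patients, and no new data. If the slopes turn out equal, well under 1% of variance is lost. Reporting the SPPB SDs and between-visit correlations from this pilot would also let the larger trial settle the question with data.
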